#### 4.2.4 Site and Researcher Information

Data of the study sites and of the Researcher will be presented in summary tables and listings.

The summary tables for site information will show absolute and relative frequencies for the institution type (private practice/ private hospital, general hospital, academic/ university hospital, other), the type of unit (general population, transplant, drug user, HIV/ HCV co-infection, hepatocellular carcinoma [HCC]), and the site location (urban, rural). Regarding type of unit multiple answers per site are possible.

The principle researcher experience will be summarized by presenting for each therapeutic specialty (hepatology, infectious disease, gastroenterology, internal medicine, transplant, general practitioner) the number and percentage of principle researchers, who have the specific experience. Furthermore, the number and percentage of sites with at least one researcher (i.e. including co-researcher) of the therapeutic specialty concerned and the number of HCV-infected patients typically seen per month at the site (<25, 25-50, 51-75, 76-100, >100), including the patients seen by co-researcher, will be summarized. Note: Multiple therapeutic specialties could be reported per researcher.

An overview of Tables for site and researcher information is given in Table 5.

Table 5 Overview of Outputs for Site and Researcher Information

Output Title	Output Short Name	Analysis Population
Site Information - <country></country>	tsi_ <c></c>	Sites with patients
Researcher Experience- <country></country>	tre_ <c></c>	Sites with patients

The layouts of the tables mentioned above are provided in Part II of the SAP (Table Shells).

# 4.2.5 Patient Disposition

The frequencies of patients belonging to the different populations (i.e. EP, TP, CP, CPSFU; SP) will be summarized by genotype and cirrhosis status and overall using the EP analysis groups as specified in section 4.2.1. The reasons for exclusion from a particular population will be also summarized in the frequency tables. Additionally, information on patient disposition will be listed.

Furthermore the frequency of patients not completing the study as defined per protocol (i.e. no HCV RNA assessment performed at least 10 weeks post-treatment), will be summarized by treatment regimen and cirrhosis status and additionally by genotype and cirrhosis status and overall for the SP and CP. The reasons for not completing the study as entered on the CRF will be displayed (i.e. failure to return, insufficient virological response (HCV RNA detectable at End of treatment, Relapse post-treatment), patient never started treatment, withdrawn consent, death, other).

Additionally, the main reason for early termination of the ABBVIE regimen (AE or SAE [Physician decision], virological non-response [Physician decision], rebound or breakthrough [Physician decision], resistance to DAA [Physician decision], patient refused to continue treatment, patient withdrew consent to participate in the study, lost to follow-up, other, unknown [if actual duration is shortened for more than 7 days]) and Ribavirin (Anemia, Nausea/Vomiting, Rash, Other) will be summarized by treatment regimen and cirrhosis status and additionally by genotype and cirrhosis status and overall for the following different analysis populations: CP and SP.

Finally the study regimens assigned at baseline will be summarized (a) by genotype and cirrhosis status and (b) by genotype and pre-treatment status (treatment naïve vs treatment experienced) for CP and SP.

An overview of Tables is given in Table 6.

Table 6 Overview of Outputs for Patient Disposition

Output Title	Output Short Name	Analysis Population
Patient Disposition by Genotype and Cirrhosis Status – EP - <country></country>	tdis_ <c>_gc_ep</c>	Patients Enrolled
Listing of Patient Disposition - EP- <country></country>	ldis_ <c>_ep</c>	Patients Enrolled
Premature Termination of the Study and its Main Reason by <treatment genotype="" regimen=""> and Cirrhosis Status - CP - <country></country></treatment>	tps_ <c>_<t g="">c _cp</t></c>	Core population
Premature Termination of the Study and its Main Reason by <treatment genotype="" regimen=""> and Cirrhosis Status - SP - <country></country></treatment>	tps_ <c>_<t g="">c _sp</t></c>	Safety population
Premature Termination of Treatment and its Main Reason by <treatment genotype="" regimen=""> and Cirrhosis Status - CP - <country></country></treatment>	tpt_ <c>_<t g="">c _cp</t></c>	Core population
Premature Termination of Treatment and its Main Reason by <treatment genotype="" regimen=""> and Cirrhosis Status - SP- <country></country></treatment>	tpt_ <c>_<t g="">c _sp</t></c>	Safety population
Treatment Regimen by Genotype and Cirrhosis Status - CP - <country></country>	ttr_ <c>_gc _cp</c>	Core population
Treatment Regimen by Genotype and Cirrhosis Status - SP - <country></country>	ttr_ <c>_gc _sp</c>	Safety population
Treatment Regimen by Genotype and Pretreatment Status - CP - <country></country>	ttr_ <c>_gpe_cp</c>	Core population
Treatment Regimen by Genotype and Pretreatment Status - SP - <country></country>	ttr_ <c>_gpe_sp</c>	Safety population

The layouts of the tables mentioned above are provided in Part II of the SAP (Table Shells).

#### 4.2.6 Baseline Characteristics

All baseline and disease characteristics will be summarized for the CP stratified by genotype and cirrhosis status and overall, in accordance with the CP analysis groups specified in section 4.2.1). Corresponding baseline summaries will be repeated for the TP. In addition, these characteristics will be summarized by cirrhosis status and treatment regimen and overall for the SP, in accordance with the SP analysis groups specified in section 4.2.1. Summary statistics (n, mean, median, standard deviation [SD], minimum, maximum) will be generated for continuous variables (e.g. age and body mass index [BMI]). The number and percentage of patients will be presented for categorical variables (e.g. gender and race).

#### 4.2.6.1 Socio-demographic characteristics

Demographic data will be summarized in a table displaying:

- Age (continuous and grouped by 18-65, 66-84, >=85 years)
- Gender (Male, Female)

- Race/ Ethnic Origin (White/Caucasian, Black, Asian/Oriental, Native American/American Indian, Other)
- Interleukin 28B (IL28B) genotype, rs12979860 (CC, CT, TT, Unknown)
- Interleukin 28B (IL28B) genotype, rs8099917 (TT,TG, GG, Unknown)
- Height [cm]
- Weight [kg]
- BMI [kg/m²]

An overview of Tables for site and researcher information is given in Table 7.

#### 4.2.6.2 CHC disease characteristics

CHC disease characteristics will be summarized in a table displaying:

- Years since diagnosis of HCV infection
- Mode of HCV Infection (Drug use (i.v.), Drug use (non i.v.), Sexual transmission,
   Occupational [HCV acquired while doing his/her job, e.g. physicians or nurses], Blood
   transfusion or transplantation, Perinatal, Contaminated medical device [other than i.v.
   drug use], Other, Unknown)
- Pretreatment Status (Naïve, Experienced)
- HCV Genotype and Subtype (as recorded in the CRF)
- Most recent stage of liver fibrosis (No cirrhosis, Transition to cirrhosis, Cirrhosis) [Only
  one method should be selected by the physicians to report stage of fibrosis. If
  nevertheless, there are multiple methods reported, the priority of the results of the
  assessments is as follows:1. biopsy, 2. non-invasive, 3. clinical/best guess. For biopsy as
  assessment method the respective categories are defined as follows:
  - o No cirrhosis is defined by No fibrosis, Mild/minimal fibrosis, Moderate fibrosis
  - Transition to cirrhosis is defined by Advanced Fibrosis
  - o Cirrhosis is defined by Cirrhosis]
- Assessment method for liver fibrosis staging (Biopsy, Non-invasive, Clinical/Best guess)
   [If multiple answers are ticked, the priority is as follows: biopsy, non-invasive, clinical/best guess.]
- Time between treatment start and biopsy assessment [months] (continuous)
- Time since biopsy [months] (categorized as ≤3, >3-6, >6-12, >12-24, >24-60, >60 months)
- Metavir fibrosis score (0, 1, 2, 3, 4)
- Ishak fibrosis score (0, 1, 2, 3, 4, 5, 6)
- Batts/Ludwig fibrosis score (0, 1, 2, 3, 4)
- Knodell fibrosis score (0, 1, 3, 4)
- Scheuer fibrosis score (0, 1, 2, 3, 4)
- Time between treatment start and FibroScan assessment [months] (continuous)
- Time since FibroScan [months] (categorized as ≤1, >1-2, >2-6, >6-12, >12-24, >24 months)
- FibroScan [kPa] (<8.8, 8.8-<9.6, 9.6-<14.6, ≥14.6)
- Time between treatment start and ARFI assessment [months] (continuous)
- Time since ARFI [months] (categorized as ≤1, >1-2, >2-6, >6-12, >12-24, >24 months)
- AFRI [m/s]

- Time between treatment start and FibroTest assessment [months] (continuous)
- Time since FibroTest [months] (categorized as ≤1, >1-2, >2-6, >6-12, >12-24, >24 months)
- Results of FibroTest (<=0.21, 0.22-0.27, 0.28-0.31, 0.32-0.48, 0.49-0.58, 0.59-0.72, 0.73-0.74, >=0.75)
- Esophageal varices (Yes, No, Unknown)
- History of liver decompensation (No never decompensated, Yes but currently compensated, Yes still decompensated [including patients with a Child Pugh Score >=7], Current signs/symptoms Total, Current signs/symptoms Coagulopathy, Current signs/symptoms Hyperbilirubinemia, Current signs/symptoms Hepatic encephalopathy, Current signs/symptoms Hypo-albuminemia, Current signs/symptoms Ascites, Current signs/symptoms Bleeding from esophageal varices [multiple answers are possible])
- Child Pugh Score (categorized as 5-6, 7-9, 10-15)

An overview of Tables for site and researcher information is given in Table 7.

## 4.2.6.3 CHC treatment history

For treatment-experienced patients the most recent prior treatment and the outcome to prior treatment as reported by the investigator in the eCRF (Null response, Partial response, Breakthrough, Relapse, Sustained virological response (SVR) followed by reinfection, Discontinued [and none of the above], Unknown/ None of the above) will be summarized in frequency tables. In addition to the frequency of each medication (IFN alpha, PEG IFN-alpha, IFN NOS, PEG IFN NOS, Ribavirin, DAA), the frequency of the combinations (pegIFN alpha + RBV, pegIFN alpha + RBV + Telaprevir, XXX) will be summarized.

#### 4.2.6.4 Co-morbidities and co-infections

A summary table will present the absolute and relative frequencies of HCV co-infections, CHC related comorbidities and other co-morbidities, in more detail:

- HCV Co-infections
  - Human immunodeficiency virus (HIV)
  - Hepatitis B virus (HBV)
  - o Tuberculosis
  - Schistosomiasis
- Liver and/ or CHC related co-morbidities
  - Liver transplantation
  - Hepatocellular carcinoma
  - Steatosis (non-alcoholic)
  - Alcoholic liver disease
  - Primary biliary cirrhosis

- Auto-immune hepatitis
- Wilson disease
- Cryoglobulinemia
- Porphyria cutanea tarda (PCT)
- o Auto-immune skin disease

#### Other co-morbidities

- Kidney transplant
- Chronic kidney disease (Mild, Moderate, Severe, Currently on dialysis, Currently not on dialysis)
- Psychiatric disorders (Depression, Bipolar disorder, Schizophrenia, Personality disorder)
- Diabetes mellitus (Type 1, Type 2)
- o Insulin resistance
- Metabolic syndrome
- Lipid disorder
- o Hyperthyroidism
- Hypothyroidism
- Cardiovascular disease (Myocardial infarction, Angina pectoris, Hypertension, Stroke)
- Immunologically mediated disease
- o Hemophilia
- o Thalassemia
- o Sickle cell anemia
- o V. Willebrand disease
- Psychoactive substance dependency (Active injection drug use, Inhalate cocaine, Marihuana/ cannabis, Opiate substitution)
- o Other

The patient's alcohol consumption will be displayed in a further table, i.e.:

- Alcohol use (None, Yes occasional, Yes regular, Ex-drinker [6 units/drinks per day, none in the last 3 months])
- Average number of units/drinks per week (if regular alcohol use is reported)

One unit/drink is defined as 10 milliliters (or approximately 8 grams) of pure alcohol and equals: 200 ml of beer or 100 ml of wine or 20 ml of hard liquor. An overview of Tables and Listings for the above mentioned variables is given in Table 7.

#### 4.2.6.5 CHC related and other laboratory data at baseline

The laboratory data at baseline are the most recent available data prior to first administration of the ABBVIE REGIMEN (including day 1, see Table 4). All reported clinical laboratory test results will be assigned to one of the time points using the time windows specified in the Table 4.

A summary table will show CHC related laboratory data at baseline, i.e. HCV RNA in IU/mL, HCV RNA in log10 IU/mL, and HCV RNA categorized using 400,000, 800,000, 6,000,000 and 10,000,000 as cut-offs, ALT, ALT ratio, AST, AST ratio, APRI, FIB-4. ALT-ratio, AST ratio, APRI and FIB-4 will be calculated as follows:

ALT ratio = ALT value / upper limit of normal (ULN) of local laboratory

AST ratio = AST value / ULN of local laboratory

APRI =  $100 \times AST [IU/L] / (ULN of AST [IU/L] * Platelets [<math>10^9/L$ ]) (APRI= aspartate aminotransferase to platelet ratio index [1]; calculated, if laboratory assessments took place within 30 days)

FIB-4 = (Age [years] x AST [IU/L]) / (Platelets [10^9/L] \* Square root of ALT [IU/L]) (FIB-4= Fibrosis 4 index [2]; calculated, if laboratory assessments took place within 30 days)

In addition the following other key laboratory data at baseline will be summarized:  $\gamma$ -GT, total bilirubin, albumin, creatinine, creatinine clearance (continuous and categorize as Grade 1 [60-<LLN mL/min], Grade 2 [30-<60 mL/min], Grade 3 [15-<30 mL/min], Grade 4 [<15 mL/min]; if LLN is missing 75 mL/min is used), AFP, hemoglobin, platelets, prothrombin time, and INR (if documented instead of prothrombin time). The creatinine clearance will be calculated as follows:

Creatinine clearance [ml/min] =  $(140\text{-age})^*$ Weight (in kg)\*constant/Creatinine (in  $\mu$ mol/L) (constant is 1.23 for men and 1.04 for women; calculated by Cockcroft-Gault-Formula)

A further table CD4 and HIV-RNA test results are displayed for patients with HIV only.

An overview of Tables for the above mentioned variables is given in Table 7.

Table 7 Overview of Outputs for Baseline Characteristics

Output Title	Output Short Name	Analysis Population
Socio-demographic Characteristics by Genotype and Cirrhosis Status - CP - <country></country>	tdm_ <c>_gc_cp</c>	Core population
Socio-demographic Characteristics by Genotype and Cirrhosis Status - TP - <country></country>	tdm_ <c> _gc_tp</c>	Target population
Socio-demographic Characteristics by Treatment Regimen and Cirrhosis Status - SP - <country></country>	tdm_ <c>_tc_sp</c>	Safety population
CHC Disease Characteristics by Genotype and Cirrhosis Status - CP - <country></country>	tdc_ <c>_gc_cp</c>	Core population
CHC Disease Characteristics by Genotype and Cirrhosis Status - TP - <country></country>	tdc_ <c>_gc_tp</c>	Target population
CHC Disease Characteristics by Treatment Regimen and Cirrhosis Status - SP - <country></country>	tdc_ <c>_tc_sp</c>	Safety population
CHC Related Laboratory Variables at Baseline by Genotype and Cirrhosis Status - CP - <country></country>	tlcdb_ <c>_gc_cp</c>	Core population
CHC Related Laboratory Variables at Baseline by Genotype and Cirrhosis Status - TP - <country></country>	tlcdb_ <c> _gc_tp</c>	Target population
CHC Related Laboratory Variables at Baseline by Treatment Regimen and Cirrhosis Status - SP - <country></country>	tlcdb_ <c>_tc_sp</c>	Safety population
Other Key Laboratory Variables at Baseline by Genotype and Cirrhosis Status - CP - <country></country>	tkldb_ <c>_gc_cp</c>	Core population
Other Key Laboratory Variables at Baseline by Genotype and Cirrhosis Status - TP - <country></country>	tkldb_ <c> _gc_tp</c>	Target population
Other Key Laboratory Variables at Baseline by Treatment Regimen and Cirrhosis Status - SP -	tkldb_ <c>_tc_sp</c>	Safety population
<country> CHC Treatment History in Treatment Experienced Patients by Genotype and Cirrhosis Status - CP -</country>	tth_ <c>_gc_cp_ep</c>	Core population: treatment-experienced
<country> CHC Treatment History in Treatment Experienced Patients by Genotype and Cirrhosis Status - TP -</country>	tth_ <c>_gc_tp_ep</c>	patients Target population: treatment-experienced
<country> CHC Treatment History in Treatment Experienced Patients by Treatment Regimen and Cirrhosis Status -</country>	tth_ <c>_tc_sp_ep</c>	patients Safety population: treatment-experienced
SP - <country> Co-morbidities and Co-infections by Genotype and Cirrhosis Status - CP - <country></country></country>	tcoi_ <c>_gc_cp</c>	patients Core population
Co-morbidities and Co-infections by Genotype and Cirrhosis Status - TP - <country></country>	tcoi_ <c> _gc_tp</c>	Target population
Co-morbidities and Co-infections by Treatment Regimen and Cirrhosis Status - SP - <country></country>	tcoi_ <c>_tc_sp</c>	Safety population

Alcohol Consumption by Genotype and Cirrhosis Status - CP - <country></country>	tac_ <c>_gc_cp</c>	Core population
Alcohol Consumption by Genotype and Cirrhosis Status - TP - <country></country>	tac_ <c> _gc_tp</c>	Target population
Alcohol Consumption by Treatment Regimen and Cirrhosis Status - SP - <country></country>	tac_ <c>_tc_sp</c>	Safety population
CD4 and HIV RNA in Patients with HIV at Baseline by Genotype and Cirrhosis Status - CP - <country></country>	tlchb_ <c>_gc_cp_hiv</c>	Core population: patients with HIV
CD4 and HIV RNA in Patients with HIV at Baseline by Genotype and Cirrhosis Status - TP - <country></country>	tlchb_ <c> _gc_tp_hiv</c>	Target population: patients with HIV
CD4 and HIV RNA in Patients with HIV at Baseline by Treatment Regimen and Cirrhosis Status - SP - <country></country>	tlchb_ <c>_tc_sp_hiv</c>	Safety population: patients with HIV

The layouts of the tables mentioned above are provided in Part II of the SAP (Table Shells).

# 4.2.7 Analyses of the Objectives

#### 4.2.7.1 Primary Effectiveness Variable

The primary objective of this study is to estimate the SVR12 rates in HCV patients treated according to the ABBVIE Regimen.

Therefore the simple percentage of patients achieving SVR12 (for definition see section 4.1.1) will be calculated and a two-sided 95% confidence interval (CI) of the percentage will be computed based on the Wilson's Score method.

The primary effectiveness analysis on clinical outcomes will be performed on all patients in the CP stratified by genotype and cirrhosis status and overall.

In the framework of sensitivity analyses the primary analyses will be repeated for the CPSFU . Furthermore, the SVR12 rates will be also determined for all patients of the NCP.

An overview of Tables is given in Table 8.

The layouts of the tables mentioned above are provided in Part II of the SAP (Table Shells).

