Descriptive and exploratory statistical methods will be used to analyze the data of the study. All baseline and disease characteristics will be summarized for the CP stratified by the CP analysis groups (based on genotype 1 subtype, fibrosis status, treatment experienced or naïve), which are relevant for scheduled treatment combination (\pm dasabuvir, \pm RBV) and duration (12 or 24

Confidential Information

No use or disclose outside AbbVie is permitted without prior written authorization from AbbVie

weeks). In addition, baseline summaries will be repeated for the SP and TP without stratification into subgroups. Further details of analysis populations and the CP analysis groups will be specified in the statistical analysis plan (SAP).

The primary effectiveness analysis will be performed for CP patients, stratified by the CP analysis groups. Response rates (i.e. SVR12 rate, end of treatment [EoT] response rate, relapse rate, viral breakthrough) will be determined for the various CP analysis groups. The relapse rates will be estimated in patients of the CP analysis groups with EoT response and sufficient HCV RNA measurements post treatment. Viral breakthrough rates will be estimated in all patients of the CP analysis groups, who have at least one undetectable HCV RNA measurement on treatment and at least one on-treatment or EoT measurement thereafter. For all rates specified above 95%-confidence intervals (CIs) will be determined using the Clopper-Pearson method.

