9.7.3.3 Statistical Methods for Analysis of Effectiveness Variables

The simple percentage of patients achieving SVR12 will be calculated and an exact two-sided 95% confidence interval (CI) of the percentage will be computed based on the Clopper-Pearson method.

Corresponding methods will be used for other response rates (EoT response rate, relapse rate, viral breakthrough). The relapse rates will be estimated in patients of the CP analysis groups with EoT response and sufficient HCV RNA measurements post-treatment. Viral breakthrough rates will be estimated in all patients of the CP analysis groups, who have at least one undetectable HCV RNA measurement on-treatment and at least one on-treatment or EoT measurement thereafter.

Univariate and multiple logistic regression (MLR) methods will be used to investigate the impact of the following explanatory covariates on SVR12:

- Key demographic information
- Mode of CHC infection
- HCV RNA level at baseline
- Most recent stage of liver fibrosis
- HCV genotype and subtype (if available)
- Type of treating institute
- Liver and/or CHC related co-morbidities
- Key clinical chemistry and hematology laboratory variables at baseline
- In treatment experienced patients only:
 - Most recent prior treatment for CHC
 - Outcome of most recent prior CHC treatment

Further details and additional covariates will be specified in the SAP.

These analyses will be of exploratory nature, data driven, and will be repeatedly performed for various CP Analysis Groups, since not each covariate might be

predictive in each patient group. Furthermore, the fact that treatment regimens will differ in the various patient groups has to be taken into account, when selecting the patient groups for each MLR analysis. Backward selection procedures will be applied to generate the final MLR models which consider only covariates in the selection procedure with a p-value <0.25 in the corresponding univariate logistic regression analysis. A p-value <0.05 will be used for the covariates to stay in the model in a backward elimination step. Logistic regression methods will also be used to investigate the impact of treatment adherence on SVR12.

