# 3.2 Sample Size Calculation

In phase III studies investigating the interferon-free ABBVIE REGIMEN  $\pm$  RBV, SVR12 rates of at least 90% were observed, even in difficult-to-treat CHC patients (e.g. cirrhotic G1a treatment experienced patients). It is expected that 400 patients treated with the ABBVIE REGIMEN  $\pm$  RBV can be included into this observational study during the planned inclusion period of 6 months, and that about 90 to 95% of the patients enrolled will be evaluable in the core population (see Section 4.2.1 for the definition of the core population). As shown in Table 1, if the SVR12 rate is at least 90% and there are 360-380 evaluable patients, then the width of the 95% confidence interval (CI) will not be wider than 6.5%. If the SVR12 rate is at least 95% and there are 360-380 evaluable patients, then the 95% CI will have a width of less than 5%. With at least 340 evaluable patients the width is still less than 5%, if the SVR12 rate is at least 95%.

Number of	SVR12 rates	95% Confidence Interval*			
patients		Lower Limit	Upper Limit	Width	
340	90%	86.3	93.0	6.7%	
340	95%	92.1	97.1	4.9%	
360	90%	86.4	92.9	6.5%	
360	95%	92.2	97.0	4.8%	
380	90%	86.5	92.8	6.3%	
380	95%	92.3	97.0	4.7%	

Table 1 Width of 95% Confidence Interval for SVR12

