#### CP analysis groups and related treatment regimens

The CP analysis groups are defined according to the patient's fibrosis status and genotype/subtype. The standard summaries by CP analysis groups in the CP and CPSFU population are structured follows (is not specified otherwise):

- Total (regardless of cirrhosis status)
  - (1) Total (regardless of genotype)
  - (2) G1 (Total)
  - (3) G1a (including mixed subtypes and patients with unknown subtype)
  - (4) G1b
  - (5) G4 (non-G1)
- Patients with cirrhosis
  - (6) Total (regardless of genotype)
  - (7) G1 (Total)
  - (8) G1a (including mixed subtypes and patients with unknown subtype)
  - (9) G1b
  - (10) G4 (non-G1)
- Patients without cirrhosis
  - (11) Total (regardless of genotype)
  - (12) G1 (Total)
  - (13) G1a (including mixed subtypes and patients with unknown subtype)
  - (14) G1b
  - (15) G4 (non-G1)

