# 4.2.7.2 Secondary Variables

# 4.2.7.2.1 Secondary Effectiveness Variables

#### Response

For the other response rates (i.e. RVR, SVR24, EoT response rate, relapse rate, viral breakthrough), the simple percentage of patients and a two-sided 95% confidence interval (CI) of the percentage will be computed (based on the Wilson's score method) as well. The RVR and EoT response rates will be reported for CP and the SVR24 rate will be reported for the respective CPSFU, stratified by genotype and cirrhosis status and overall. The relapse rates will be estimated stratified by SVR window (i.e. during SVR12 window=relapse12, during SVR24

window=relapse24) and stratified by genotype and cirrhosis status and overall in patients of the CP with EoT response who fulfilled the following criteria:

- completed treatment as defined previously.
- had at least one HCV RNA measurement >= 70 days post-treatment or was a treatment failure between EoT and 70 days post-treatment.

Viral breakthrough rates [defined as at least one documented HCV RNA <50 IU/mL followed by HCV RNA ≥50 IU/mL during treatment] will be estimated overall and stratified by genotype and cirrhosis status in all patients of the CP, who have at least one undetectable or unquantifiable, ontreatment HCV RNA measurement and at least one on-treatment or EoT measurement thereafter.

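### Does the SAP's unannounced switch from Clopper-Pearson to Wilson intervals for SVR12 and the other response rates require a correction?

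*SAP*

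**What the plan says.** The protocol names the exact method twice. Its Abstract closes the list of rates (SVR12, end-of-treatment response, relapse, breakthrough) with "For all rates specified above 95%-confidence intervals (CIs) will be determined using the Clopper-Pearson method". Section 9.7.3.3 says of SVR12 that "an exact two-sided 95% confidence interval (CI) of the percentage will be computed based on the Clopper-Pearson method" and applies corresponding methods to the other three rates.

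The SAP names a different method. Section 4.2.7.1 says of SVR12 that "a two-sided 95% confidence interval (CI) of the percentage will be computed based on the Wilson's Score method". Section 4.2.7.2.1 says that for the remaining rates, to which it adds RVR and SVR24, the interval "of the percentage will be computed (based on the Wilson's score method) as well".

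The intervals are not confined to the whole core population: "The primary effectiveness analysis on clinical outcomes will be performed on all patients in the CP stratified by genotype and cirrhosis status and overall". SAP 4.2.1 lists 15 core-population groups. Under its interim section (4.2.9) the analyses are repeated in patients who started before 1 April 2016 with a planned 12-week course.

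The precision table in SAP 3.2 (Table 1) carries a Clopper-Pearson footnote.

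**The concern.** The primary analysis is a percentage with a confidence interval, so the interval method is one of the few statistical choices that matter, and the protocol had already made it. The SAP changes it without comment. Elsewhere the SAP does announce departures: the 126-day upper bound of the SVR12 window in 4.1.1, and the replacement of shift tables in 4.2.8.4. The silence here therefore looks like an oversight. Precision is also planned with one method and reported with another.

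Two things would be at stake. Wilson intervals are usually narrower than exact ones at high response rates in small groups, so genotype-by-cirrhosis results could look more precise than the protocol intended. Wilson also lacks the exact method's guarantee of at least 95% coverage.

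**Working it through.** **Inputs.** Sizes 340, 360 and 380 and rates 90% and 95% come from Protocol Table 3, which is the same as SAP Table 1. Subgroup sizes are not given in either document, so I take 10 to 50 as an assumption.

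**Formulas.** With x responders out of n:
- Clopper-Pearson: lower = 2.5% quantile of Beta(x, n−x+1); upper = 97.5% quantile of Beta(x+1, n−x).
- Wilson, with p = x/n and z = 1.96: centre = (p + z²/2n)/(1 + z²/n); half-width = z·√(p(1−p)/n + z²/4n²)/(1 + z²/n).

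**The plan's own table, then Wilson.** Example for 324/360 under Wilson: centre = (0.9 + 0.005335)/1.010671 = 0.8958; half-width = 1.96 × √(0.00025 + 0.0000074)/1.010671 = 0.0311; limits 86.47 to 92.69.

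| x/n | Exact limits | Exact width | Wilson limits | Wilson width |
|---|---|---|---|---|
| 306/340 | 86.31–92.97 | 6.67 | 86.35–92.76 | 6.40 |
| 323/340 | 92.12–97.06 | 4.95 | 92.14–96.86 | 4.72 |
| 324/360 | 86.43–92.90 | 6.47 | 86.47–92.69 | 6.22 |
| 342/360 | 92.21–97.01 | 4.80 | 92.24–96.81 | 4.58 |
| 342/380 | 86.53–92.83 | 6.29 | 86.57–92.63 | 6.06 |
| 361/380 | 92.30–96.96 | 4.66 | 92.32–96.78 | 4.45 |

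The exact columns reproduce all six printed rows (323/340 is 4.946 before rounding, printed as 4.9). Under Wilson the lower limit rises by 0.02 to 0.04 points, the upper falls by 0.19 to 0.22, and the width shrinks by 0.21 to 0.26. The statements in SAP 3.2 (at most 6.5% at 90%, below 5% at 95%) remain true.

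**Small groups (sizes assumed).**

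| x/n | Exact | Wilson | Lower shift | Upper shift |
|---|---|---|---|---|
| 10/10 | 69.2–100 | 72.2–100 | +3.10 | 0 |
| 9/10 | 55.5–99.7 | 59.6–98.2 | +4.09 | −1.53 |
| 8/10 | 44.4–97.5 | 49.0–94.3 | +4.63 | −3.15 |
| 18/20 | 68.3–98.8 | 69.9–97.2 | +1.59 | −1.55 |
| 27/30 | 73.5–97.9 | 74.4–96.5 | +0.91 | −1.35 |
| 36/40 | 76.3–97.2 | 76.9–96.0 | +0.61 | −1.17 |
| 40/40 | 91.2–100 | 91.2–100 | +0.05 | 0 |
| 45/50 | 78.2–96.7 | 78.6–95.7 | +0.45 | −1.02 |

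Across all observed rates of 85% or more, the largest group in which any limit moves by at least 3 points is n = 12; by at least 2 points, n = 20; by at least 1 point, n = 60. The largest movement is 2.0 points at n = 20, 1.6 at n = 30 and 1.1 at n = 50.

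**How many cells could be that small.** SAP 4.2.1 says "The CP analysis groups are defined according to the patient's fibrosis status and genotype/subtype". The 15 groups are 3 blocks (all, cirrhosis, no cirrhosis) of 5 rows. Only 2 × 3 = 6 are genotype-by-cirrhosis cells (G1a, G1b and G4, each with and without cirrhosis); the other nine are pooled. Outside the core population, "Furthermore, the SVR12 rates will be also determined for all patients of the NCP", and SAP 3.2 expects that "about 90 to 95% of the patients enrolled will be evaluable in the core population". That suggests about 400 × 0.05 = 20 to 400 × 0.10 = 40 non-core patients, if all enrolled patients are in the target population. At such sizes and rates of 85% or more no limit moves by more than about 2 points.

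**Coverage.** Exact binomial enumeration over n = 10 to 50 (41 sizes) and ten of the SVR12 rates quoted in Protocol 7.1 (90, 91, 92, 93, 95, 96, 97, 98, 99 and 99.5%) gives 410 combinations. Wilson ranges from 83.9% to 98.6%, mean 95.1%; 39% of combinations are below 95% and 25 of 410 (6%) below 90%. Of those 25, 21 have a true rate of 99% or more, and the other four lie between 89.4% and 90.0%. Clopper-Pearson ranges from 95.2% to 99.9%, mean 98.7%.

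**The case for a change.** The strongest case for acting is that this is the primary interval, that the protocol settled the method, and that section 9.7.3.3 left only further details and additional covariates to the SAP. The undeclared change also has a consistent direction at the lower limit: for n from 5 to 45 and observed rates of 80 to 100%, Wilson's lower limit is always the higher one (the first exception is 46/46). For relapse the mirror image holds; the upper limit for 1/10 falls from 44.5% to 40.4%. Interim groups can only be the same size or smaller. Wilson's coverage does dip below 90% in places, and Clopper-Pearson's never falls below 95%.

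The textual conflict and the missing announcement stand. The rest weighs less than it seems. Wilson lowers the upper limit as well, and at 90% observed response from about n = 30 that is the larger movement (36/40: +0.61 and −1.17), so the switch does not simply flatter the regimen. The worst coverage (83.9%) occurs at a true rate of 99.5% with n = 35, and nearly all values below 90% are at true rates of 99% or more. Averaged over the realistic range Wilson is on target, whereas the exact method's guarantee costs width: 44.2 − 38.6 = 5.6 points at 9/10.

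The mismatch with SAP Table 1 does no harm. The table is correctly labelled, and in all six rows the reported Wilson interval would be narrower than the planning width, so the table errs on the safe side.

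**Conclusion.** No change to the plan is needed. The protocol and SAP do disagree and the SAP text does not say so, but this is a documentation lapse. An analyst who follows the SAP as written knows which interval to compute and obtains a sound one, fixed in advance of the interim that the SAP schedules for the first quarter of 2017. Returning to Clopper-Pearson would be a fair trade-off and not a repair: guaranteed coverage (mean 98.7%) against narrower intervals with coverage near nominal on average (mean 95.1%). A sentence declaring Wilson would alter no result.

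Overall the effect is at most 0.22 points on any limit in the tabulated cases. In subgroups it reaches 3 points only at 12 patients or fewer, for observed rates of 85% or more; in such groups the interval is wide under either method (9/10: 44 against 39 points), and the reading is the same. The objective is to describe SVR12, and no hypothesis, margin or decision rule depends on a limit.

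This rests on assumed subgroup sizes of 10 to 50, since the documents give none, and on high response rates as quoted in Protocol 7.1. In cells smaller than 10 the limits would move further (5/5: lower limit 47.8% exact, 56.6% Wilson), but neither interval would support a firm statement there. The table shells in Part II of the SAP were not available, so the absence of a declaration refers to the SAP text alone.
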